7 STUDY POPULATION

Patients planned for breast surgery and SLNB, will be considered for enrolment.

7.1 Inclusion criteria

1. Age above 18 years
2. Planned for sentinel lymph node biopsy at (or after) breast surgery
3. Signed and dated written informed consent before the start of specific protocol procedures

7.2 Exclusion criteria

A patient meeting ANY of the following criteria is not eligible for study participation:

1. Pregnant or breast-feeding
2. Iron overload disease
3. Known hypersensitivity to iron, dextran compounds or blue dye.
4. Inability to understand given information and give informed consent or undergo study procedures

7.3 Subject enrolment

Subject eligibility will be established before enrolment. Subjects will be enrolled strictly sequentially, as subjects are eligible for study participation. After enrolment the subject will be given a unique subject number per site, consisting of three letters for the study, the following three letters for the site and then a lot number, i.e., MAGGBG001. If a subject discontinues from the study, the subject number will not be reused, but the subject may be replaced.

7.4 Discontinuation criteria for individual subjects

The subject is free to withdraw from the study for any reason and at any time without giving reason for doing so and without penalty or prejudice to their treatment. The investigator is also free to terminate a subject's study treatment at any time if the subject's clinical condition warrants it.

Discontinuation Criteria for Individual Subjects:

Subjects must be discontinued from the study for the following reasons:

1. Inappropriate enrolment (violation of Inclusion / Exclusion Criteria)
2. Withdrawal of consent
3. Due to safety reasons judged by the Investigator.

The reasons for discontinuation should be recorded in the case report form (CRF). Persons discontinued from the study will be asked to return for an "End of Treatment Visit" and will thereafter be taken care of and followed at the discretion of the treating physician. Persons who discontinue the study will be replaced. Data collected up to the moment of withdrawal will be a part of the study analysis if accepted by the person.

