6.2 Study endpoints

Primary endpoint:

SLN detection rate for Magtrace® 0.1ml and for the dual technique (Tc⁹⁹ +/- blue dye) measured as per cent of patients where a SLN is identified using either the magnetic or the dual technique

Secondary endpoints:

- A. MRI Magtrace® artefacts at 3-6, 12 and 24-36 months postoperatively measured as per cent of patients with remaining artefacts evaluated by blinded central review.
- B. Skin staining due to injected Magtrace® and blue dye at 4 weeks, 12, 24 and 36 months measured as per cent of patients with remaining brown or blue skin staining and stain size, evaluated by the investigator and the Skin Discoloration Impact Evaluation Questionnaire (SDIEQ)[8]
- C. Rate of device-related AEs and SAEs
- D. Numbers of nodes detected and removed for Magtrace® 0.1ml and for the dual technique (Tc⁹⁹ +/- blue dye)
- E. Concordance between detected sentinel lymph nodes by Magtrace® 0.1ml or by for the dual technique (Tc⁹⁹ +/- blue dye)

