6.4.2 Procedures

An intradermal dose of 0.1ml Magtrace® will be injected up to 30 days before surgery. The injection should be in the skin over the tumour, or at the border of the areola. A pre-operative photo of the breast will be taken, including any staining.

Before surgery Tc⁹⁹ is injected in the breast as per routine practice. Blue dye is optional and if used, it is injected after induction of anaesthesia. During surgery, SLNs are first identified with the SentiMag[®]-probe. The dual technique, with the gamma probe +/- blue dye will be used afterwards, confirming each removed SLN and for detection of additional SLNs. For each tracer, the following parameters will be recorded in the CRF: transcutaneous magnetic and radioactive signals in breast and axilla, number of nodes, the colour of the nodes, signals in vivo and ex vivo for each SLN, residual transcutaneous signals at the end of surgery in breast and axilla. A lymph node is considered a SLN if it contains more than a 10% activity compared to the maximum activity of the highest scoring lymph node (first SLN) with either tracer. Each SLN will be sent separately for routine histopathology with the specific question concerning microscopically detected SPIO. For all patients, the pathologists are requested to report the lymph node status separately.

At the first post-operative visit (approximately 4 weeks after surgery) blue and brown skin staining will be recorded by photography including a centimetre scale, and any residual magnetic signal will be measured in the breast. In those patients with a remaining skin staining this procedure will be repeated at 12 months, and after 24 and 36 months by telephone interview without a photo or a physical visit. Patients will be asked about how they experience the staining according to a 5-point Likert scale (Skin Discoloration Impact Evaluation Questionnaire (SDIEQ))[8].

In up to 50 patients, a postoperative routine MRI of the breast, with contrast medium will be performed at 3-6, 12 and 24-36 months after surgery to evaluate the presence of SPIO artefacts. MRI artifacts and mammographic density will be recorded in a separate CRF by the radiologists and then transferred to our CRF.

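### Section 7.4 discontinues any patient with an eligibility violation, even after Magtrace injection, so late-found cases leave scheduled safety and staining follow-up

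*Protocol*

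**What the plan says.** Protocol section 7.4 opens its list with "Subjects must be discontinued from the study for the following reasons", and the first reason is "Inappropriate enrolment (violation of Inclusion / Exclusion Criteria". The synopsis repeats the list. Neither place sets a time limit or mentions patients who have already received the tracer.

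The same section gives the consequences. The reason goes in the CRF and the person is asked to return for one end visit, which the schedule in 6.4.3 does not list. The person "will thereafter be taken care of and followed at the discretion of the treating physician" and is to be replaced. On data, it says: "Data collected up to the moment of withdrawal will be a part of the study analysis if accepted by the person".

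Four other places bear on this:

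- Section 7.3: "Subject eligibility will be established before enrolment". The rule therefore acts only on violations that are discovered later.
- Section 7.2: three of the four exclusions plausibly concern tracer safety, namely pregnancy or breast-feeding, iron overload, and "Known hypersensitivity to iron, dextran compounds or blue dye".
- Section 6.4.2: "An intradermal dose of 0.1ml Magtrace® will be injected up to 30 days before surgery". Section 8.2 confirms that this is a single administration.
- Section 6.2, endpoint C: "Rate of device-related AEs and SAEs".

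On replacement the protocol is inconsistent. Section 7.4 makes it obligatory, while 7.3 and 11.2 make it optional.

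**The concern.** Section 7.4 treats two things as one: stopping study procedures and stopping the collection of study data. Before injection the difference hardly matters, because there is no exposure to follow. After injection it does, because leaving the study cannot undo the exposure, while it does end the protocol's scheduled observation of its effects.

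The patients concerned are those injected despite a criterion that was probably written to keep them from being injected. Their events are among the most informative for endpoint C, and the rule shortens their observation. Replacing them with eligible patients restores the number in the trial but not the missing safety information. An analysis plan can decide who is counted. It cannot recover visits that sites were told not to hold.

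**Working it through.** **1. What is lost depends on when the violation is found.**

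| Violation found | Detection result | Safety and staining follow-up |
|---|---|---|
| Before injection | No exposure, nothing lost | Nothing lost |
| Between injection and surgery (0 to 30 days) | Not collected under the protocol | 4-week visit and any later staining contacts lost, apart from one end visit |
| After surgery, before the 4-week visit | Already exists; kept if the person accepts | As in the row above |
| After the 4-week visit | Already exists; kept if the person accepts | Later contacts lost, but only if a stain remains |

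The last row follows from sections 6.4.1 and 6.4.2 and the footnote in 6.4.3: staining follow-up stops once the stain is gone. Thirty-six months is therefore a maximum.

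**2. The protocol's own sample size.** Inputs from section 11.1: detection 98% with both methods, margin 4 percentage points, one-sided 97.5% confidence limit, power 80%.

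- n = 2 × 0.98 × 0.02 × (1.960 + 0.842)² / 0.04² = 192.3, so 193 per arm and 386 in total. Both stated figures reproduce.
- Allowing for 10% dropout: 193 / 0.90 = 214.4, so 215. The stated 220 leaves room for 27 losses (27/220 = 12.3%).

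**3. How many patients.** The protocol gives no rate of late-found violations. *Assumption:* 1% to 3%, so 2.2 to 6.6 of 220, or about 2 to 7 patients. This covers all criteria, so the number with a safety-related exclusion would be smaller.

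**4. Effect on power if none is replaced.** By the protocol's formula, power = Φ(0.04 / √(2 × 0.98 × 0.02 / m) − 1.960), with m patients left.

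| Removed of 220 | m | Power |
|---|---|---|
| 0 | 220 | 85.0% |
| 2 | 218 | 84.7% |
| 4 | 216 | 84.4% |
| 7 | 213 | 83.9% |
| 11 | 209 | 83.2% |
| 27 | 193 | 80.1% |

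These rows assume that every removed patient also loses the detection result, which overstates the effect (step 1).

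**5. Effect on the primary difference.** Each patient contributes a pair of results. Losing a concordant pair (both methods detect, or neither does) leaves the difference essentially unchanged. Losing a discordant pair moves it by about 1/220 = 0.45 to 1/193 = 0.52 percentage points. With 2% failures for each method, at most 2% + 2% = 4% of pairs can be discordant. Among 7 lost pairs that is at most 7 × 0.04 = 0.28 expected. A shift of 4/220 = 1.8 to 4/193 = 2.1 points would need four lost patients who were all Magtrace-only failures. Nothing in the protocol suggests this.

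**6. Effect on endpoint C.** Under the assumption in step 3, 2/220 = 0.9% to 7/220 = 3.2% of injected patients have shortened safety observation. One unrecorded event among 220 is 0.45 points of the event rate.

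**The case against.** The case on the other side is substantial, and most of it stands.

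- *A reader might infer that discontinuation after injection removes nothing but data.* The protocol does not support that. Tc99, with or without blue dye, is given at surgery, after Magtrace, and the optional contrast MRI comes later still. Blue dye hypersensitivity is itself an exclusion. A violation found before surgery can bear on procedures still to come.
- *A reader might infer that these patients disappear from the safety record.* That is also too strong. The duty to report related serious events and relevant device deficiencies (sections 9 and 9.1.6) has no exemption for discontinued subjects. An end visit is requested, and earlier data are kept if the person accepts. What the protocol does not provide is any statement that non-serious device-related events or staining continue to be collected.
- *A reader might infer a threat to the non-inferiority result.* Steps 4 and 5 show that the effect is minor, and the dropout allowance and replacement absorb it.
- Eligibility is checked before enrolment, and only known hypersensitivity counts as a violation, so late-found cases should be few.
- Keeping every late-found case in data collection would go too far. Inclusion 3 and exclusion 4 concern consent and the capacity to give it; someone who never gave valid consent cannot simply be followed.
- The definition of a safety analysis set may sit in an analysis plan that is not shown.

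These points reduce the size of the concern and limit the remedy. They do not remove the rule, which is mandatory, without a time limit, and fixed in the protocol.

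**Conclusion.** The point holds in a limited form. Section 7.4 and the synopsis end study participation for any eligibility violation, whether or not the patient has been injected. The result is incomplete scheduled safety and staining data in exposed patients, while endpoint C is a rate of device-related events.

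The number affected is unknown and probably small: 2 to 7 of 220 if 1% to 3% is assumed. The detection result is lost only in the window of up to 30 days between injection and surgery. Power stays near 84% to 85% over that range, and the expected effect on the paired difference is negligible unless removal is related to Magtrace failure. This is a low-cost improvement to the completeness of safety data and does not put the primary analysis in doubt.

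**What to change.** In section 7.4 and the synopsis, separate the end of study procedures from the end of data collection:

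- For violations found after the Magtrace injection, record a protocol deviation. Continue adverse event and staining data collection, and use the tracer results if SLNB is done, for patients with valid consent who do not withdraw it.
- Exempt violations of inclusion 3 and exclusion 4.
- Leave the question of whether remaining procedures go ahead to the protocol's existing clinical rules. This change concerns data only.
- State that all injected patients stay in the safety reporting.
- Reconcile the replacement wording in 7.3, 7.4 and 11.2, so that it is clear whether replacement is obligatory or optional.

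The cost is a few lines of protocol text and, for a small number of patients, visits already in the schedule. The downside is a few patients with deviations in the data set; a sensitivity analysis without them addresses that.

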7.5 Premature termination of the study

The sponsor has the right to terminate the trial prematurely if there are any relevant medical or ethical concerns, or if completing the trial is no longer feasible. If such action is taken, the investigator must inform all subjects and ensure appropriate care and follow up. The reasons

for terminating the trial must be documented in detail and the Ethics Committee must be given a written explanation.

Premature termination of the trial will be considered if:

1. The risk-benefit balance for the trial subjects' changes markedly.
2. The sponsor considers that the trial must be discontinued for safety reasons.
3. Due to futility

8 STUDY TREATMENTS

8.1 Description of investigational product(s)

Magtrace[®] (Endomagetics Limited) is the magnetic tracer that is intended and calibrated for use with the SentiMag[®] device to identify SLN. It is a blackish-brown sterile suspension of SPIOs coated with carboxydextran, in a saline solution, with an iron concentration of 28mg/ml. The carboxydextran coating prevents agglomeration while maintaining biocompatibility. The Z-averaged particle diameter, including the organic coating, is 60nm (<0.25 polydispersity). The diameter enables the SLNs to selectively filter out the particles. After injection the particles drain naturally to the lymph nodes via the lymphatic system where they are physically filtered, trapped, and accumulate. This allows them to be used as a lymph node marker, which can be identified by the SentiMag[®] device. Magtrace[®] can be injected up to 30 days before SLNB. There is no evidence of anaphylaxis with interstitial tracer injection. Sentimag and Magtrace are CE-approved for SLN localisation.

Tc⁹⁹ consists of a sterile aqueous suspension of Technetium-99m labelled to human albumin aggregate particles and is used for radioactive detection of sentinel nodes. Blue dye, (Bleu Patenté V Sodique Guerbet, 25mg/ml) is a blue dye that is approved for use as a sentinel node tracer. Both are used within the context of a general license from the MPA after a license application (Licensmotivering avseende Generell humanlicens) since many years, and this is regularly updated.

8.2 Dose and administration

In this trial a low dose of Magtrace[®] 28mg/ml (0.1ml) will be injected intracutaneously at one time-point. This is different from the recommendation of 1-2 mL in the subcutaneous tissue. The rationale is that the lymphatic outflow from an intracutaneous injection is much higher, and a lower dose is then needed. This is the same type of injection that is currently used with Tc⁹⁹ and blue dye. The injection should be done slowly with a thin needle in the most superficial part of the skin, so that the tip of the needle is visible and that the Magtrace[®] creates a small spider web in the skin as it enters the lymphatic vessels.

8.3 Packaging, labelling, and handling of investigational products(s)

Magtrace[®] will be purchased by the official distributor in Sweden according to current clinical routine and stored according to manufacturer's instructions. As control, the routine use of Tc⁹⁹ and blue dye will be used according to current clinical routine. Magtrace[®] will be packaged, delivered and stored according to manufacturer's instructions and current clinical routine and accompanied with the approved study IFU.

9 SAFETY AND TOLERABILITY

Safety reporting in clinical investigations of medical devices shall be performed in line with the requirements of the Regulation (EU) 2017/745 – Medical Device Regulation (MDR) Article 80(2). The sponsor shall report, without delay to all Member States in which the clinical investigation is being conducted, all of the following by means of the electronic system referred to in MDR Article 73:

- a. any serious adverse event that has a causal relationship with the investigational device, the comparator or the investigation procedure or where such causal relationship is reasonably possible;
- b. any device deficiency that might have led to a serious adverse event if appropriate action had not been taken, intervention had not occurred, or circumstances had been less fortunate;
- c. any new findings in relation to any event referred to in points 1 and 2.

The period for reporting shall take account of the severity of the event. Where necessary to ensure timely reporting, the sponsor may submit an initial report that is incomplete followed up by a complete report.

9.1 Investigational device

The definition of an investigational device is a device that is assessed in a clinical investigation, MDR Article 2(46). An investigational device can be a non-CE marked device or a CE marked device. The definition does not differentiate between different regulatory statuses of devices. However, the reporting requirements are different depending on whether the clinical investigation is done for purposes described in Article 62, 74 or 82. The definition is understood to cover also the devices investigated in PMCF investigations, even if they are not subject to notification per Article 74.2.

9.1.1 Adverse Event (AE)

An adverse event is defined as any untoward medical occurrence experienced by or worsening of a pre-existing condition of a subject during this trial in relation to the investigational device or study procedure. The assessment whether a detected adverse event is related to the investigational product or procedure is done by the specific site investigator.

Any untoward medical occurrence, unintended disease or injury or any untoward clinical signs, including an abnormal laboratory finding, in subjects, users or other persons, in the context of a clinical investigation, whether or not related to the investigational device. This definition includes events that are anticipated as well as unanticipated events, and also includes events occurring in the context of a clinical investigation related to the investigational device, the comparator or the procedures involved.

9.1.2 Serious Adverse Event (SAE)

A serious adverse event (SAE) is any adverse event that led to any of the following: a) death, b) serious deterioration in the health of the subject, that resulted in any of the following: i. life-threatening illness or injury, ii. permanent impairment of a body structure or a body function, iii. hospitalisation or prolongation of patient hospitalisation, iv. medical or surgical intervention to prevent life-threatening illness or injury or permanent impairment to a body structure or a body function, v. chronic disease, c) foetal distress, foetal death or a congenital physical or mental impairment or birth defect.

9.1.3 Device deficiency

Any inadequacy in the identity, quality, durability, reliability, safety or performance of an investigational device, including malfunction, use errors or inadequacy in information supplied by the manufacturer.

9.1.4 Unanticipated Serious Adverse Device Effect (USADE)

An Unanticipated Serious Adverse Device Effect (USADE) is an effect which by its nature, incidence, severity or outcome has not been identified in the current risk assessment. Procedures associated with the use of a device should be addressed in the risk assessment, which makes it possible to determine whether the procedure related SAEs are Unanticipated Serious Adverse Device Effect or not. SAEs related to procedures imposed by the clinical investigation plan but not with the use of the device should not be considered Serious Adverse Device Effects.

9.1.5 Causality

The relationship between the use of the medical device (including the medical - surgical procedure) and the occurrence of each adverse event shall be assessed and categorized. During causality assessment activity, clinical judgement shall be used and the relevant documents, such as the Investigator's Brochure, the Clinical Investigation Plan or the Risk Analysis Report shall be consulted, as all the foreseeable serious adverse events and the potential risks are listed and assessed there. The presence of confounding factors, such as concomitant medication/treatment, the natural history of the underlying disease, other concurrent illness or risk factors shall also be considered. The above considerations apply also to the serious adverse events occurring in the comparison group.

For the purpose of harmonizing reports, each SAE will be classified according to four different levels of causality: 1. Not related 2. Possible 3. Probable 4. Causal relationship

The sponsor and the investigators will use the following definitions to assess the relationship of the serious adverse event to the investigational device, the comparator or the investigation procedure.

1. Not related: Relationship to the device, comparator or procedures can be excluded when: - the event has no temporal relationship with the use of the investigational device, or the procedures related to application of the investigational device; - the serious adverse event does not follow a known response pattern to the medical device (if the response pattern is previously known) and is biologically implausible; - the discontinuation of medical device application or the reduction of the level of activation/exposure - when clinically feasible - and reintroduction of its use (or increase of the level of activation/exposure), do not impact on the serious adverse event; - the event involves a body-site or an organ that cannot be affected by the device or procedure; the serious adverse event can be attributed to another cause (e.g. an underlying or concurrent illness/ clinical condition, an effect of another device, drug, treatment or other risk factors); - the event does not depend on a false result given by the investigational device used for diagnosis, when applicable; In order to establish the non-relatedness, not all the criteria listed above might be met at the same time, depending on the type of device/procedures and the serious adverse event.

2. Possible: The relationship with the use of the investigational device or comparator, or the relationship with procedures, is weak but cannot be ruled out completely. Alternative causes

are also possible (e.g., an underlying or concurrent illness/ clinical condition or/and an effect of another device, drug or treatment). Cases where relatedness cannot be assessed, or no information has been obtained should also be classified as possible.

3. Probable: The relationship with the use of the investigational device or comparator, or the relationship with procedures, seems relevant and/or the event cannot be reasonably explained by another cause.

4. Causal relationship: the serious adverse event is associated with the investigational device, comparator or with beyond reasonable doubt when: - the event is a known side effect of the product category the device belongs to or of similar devices and procedures; - the event has a temporal relationship with investigational device use/application or procedures; - the event involves a body-site or organ that - the investigational device or procedures are applied to; - the investigational device or procedures have an effect on; - the serious adverse event follows a known response pattern to the medical device (if the response pattern is previously known); - the discontinuation of medical device application (or reduction of the level of activation/exposure) and reintroduction of its use (or increase of the level of activation/exposure), impact on the serious adverse event (when clinically feasible); - other possible causes (e.g. an underlying or concurrent illness/ clinical condition or/and an effect of another device, drug or treatment) have been adequately ruled out; - harm to the subject is due to error in use; - the event depends on a false result given by the investigational device used for diagnosis, when applicable;

In order to establish the relatedness, not all the criteria listed above might be met at the same time, depending on the type of device/procedures and the serious adverse event. The sponsor and the investigators will distinguish between the serious adverse events related to the investigational device and those related to the procedures (any procedure specific to the clinical investigation). An adverse event can be related both to procedures and the investigational device. Complications caused by concomitant treatments not imposed by the clinical investigation plan are considered not related. Similarly, several routine diagnostic or patient management procedures are applied to patients regardless of the clinical investigation plan. If routine procedures are not imposed by the clinical investigation plan, complications caused by them are also considered not related. In some particular cases the event may not be adequately assessed because information is insufficient or contradictory and/or the data cannot be verified or supplemented. The sponsor and the Investigators will make the maximum effort to define and categorize the event and avoid these situations. Where an investigator assessment is not available and/or the sponsor remains uncertain about classifying the serious adverse event, the sponsor should not exclude the relatedness; the event should be classified as “possible” and the reporting should not be delayed. Particular attention shall be given to the causality evaluation of unanticipated serious adverse events. The occurrence of unanticipated events related could suggest that the clinical investigation places subjects at increased risk of harm than was to be expected beforehand.

